Clinical Trial Protocol

Document Number:		c31118084-01
EudraCT No.	2020-002054-25	
BI Trial No.	1402-0015	
BI Investigational Medicinal Product	BI 1358894	
Title	A phase I, open-label trial to investigate metabolism and pharmacokinetics of a single dose of [¹⁴ C] BI 1358894 administered as oral solution (Part 1) and multiple doses of BI 1358894 administered as film-coated tablets (Part 2) in healthy male volunteers	
Lay Title	A study in healthy men to test how BI 1358894 is taken up and handled by the body	
Clinical Phase	I	
Trial Clinical Monitor	A large rectangular area of the table is completely blacked out, redacting contact information for the Trial Clinical Monitor. Below this redacted area, the text "Phone: Fax: " is visible.	
Principal Investigator	A large rectangular area of the table is completely blacked out, redacting contact information for the Principal Investigator. Below this redacted area, the text "Phone: Fax: " is visible.	
Status	Final Protocol	
Version and Date	Version: 1.0	Date: 21 August 2020
Page 1 of 81		

Proprietary confidential information © 2020 Boehringer Ingelheim International GmbH or one or more of its affiliated companies. All rights reserved. This document may not - in full or in part - be passed on, reproduced, published or otherwise used without prior written permission
		

CLINICAL TRIAL PROTOCOL SYNOPSIS

Company name	Boehringer Ingelheim
Protocol date	21 August 2020
Revision date	Not applicable
BI trial number	1402-0015
Title of trial	A phase I, open-label trial to investigate metabolism and pharmacokinetics of a single dose of [¹⁴ C] BI 1358894 administered as oral solution (Part 1) and multiple doses of BI 1358894 administered as film-coated tablets (Part 2) in healthy male volunteers
Principal Investigator:	[REDACTED]
Trial site	[REDACTED]
Clinical phase	I
Trial rationale	The trial is intended to investigate the basic pharmacokinetics, excretion pathways and metabolism of BI 1358894 and its metabolites.
Trial objective	To investigate the basic pharmacokinetics after a single dose of BI 1358894 and its metabolites, total radioactivity including mass balance, excretion pathways and metabolism following a single oral dose of 100 mg [¹⁴ C] BI 1358894 given to healthy male subjects. To investigate the pharmacokinetics of BI 1358894 and its metabolite(s) following treatment with 100 mg BI 1358894, once daily over 21 days.
Trial design	Open-label, single period and single arm design with 2 treatment parts (Part 1 single dose with radiolabelled compound and Part 2 multiple doses with non-radiolabelled compound).

Proprietary confidential information © 2020 Boehringer Ingelheim International GmbH or one or more of its affiliated companies

Trial endpoints:	
Part 1: Primary endpoints:
- Mass balance recoveries of total radioactivity in urine and faeces- Amount of radioactivity excreted as a percentage of the administered dose (fe_{0-tz}) for urine and faeces Secondary endpoints: Assessment of the oral pharmacokinetics of [¹⁴C] BI 1358894 by calculating the following parameters:
- for total radioactivity and for BI 1358894: C_{max} and AUC_{0-tz}Part 2: Secondary endpoints:
- Pharmacokinetics of BI 1358894• AUC_{0-24} (area under the concentration-time curve of the analyte in plasma over the time interval from 0 to 24h)• C_{max} (maximum measured concentration of the analyte in plasma)• $AUC_{\tau,ss}$ (area under the concentration-time curve of the analyte in plasma at steady state over a uniform dosing interval τ)• $C_{max,ss}$ (maximum measured concentration of the analyte in plasma at steady state over a uniform dosing interval τ)
Number of subjects total entered each treatment	16 8 (per Part)
Diagnosis	Not applicable
Main criteria for inclusion	Healthy male subjects, age of 18 to 65 years (inclusive), body mass index (BMI) of 18.5 to 29.9 kg/m ² (inclusive)
Test product 1 dose mode of admin.	Carbon 14 labelled BI 1358894 ([¹⁴ C] BI 1358894) as oral solution 100 mg on Day 1 (Part 1) 
- in 10 mL oral solution (10 mg/mL) containing a radioactive dose of 3.7 MBq (100 μ Ci) Oral

Proprietary confidential information © 2020 Boehringer Ingelheim International GmbH or one or more of its affiliated companies

Test product 2	BI 1358894 film-coated tablet formulation
dose	100 mg (2x50 mg) QD (Part 2)
mode of admin.	Oral with 240 mL of water
Duration of treatment	Treatment Part 1: On Day 1, a single dose of radiolabelled oral solution (Test product 1) Treatment Part 2: Non-radiolabelled film-coated tablets (Test product 2) from Day 1 to Day 21.
Statistical methods	Descriptive statistics and graphical displays.

FLOW CHART

Flow Chart: Part 1 (Single dose)

Visit	Day	Planned time (relative to first drug administration [h:min])	Approximate clock time of actual day [h:min]	Event and comment	Safety laboratory	PK _{blood/plasma} ^{2,9}	PK _{urine} ⁵	PK _{faeces} ⁴	12-lead ECG	Vital signs (BP, PR)	Questioning for AEs and concomitant therapy
1	-21 to -2			Screening (SCR) ¹	A						
2	-1	-21:00	11:00	Admission to trial site	B ^{13,17}						
	1	-2:00	06:00		x ^{3,8,16}	x ³	x ³	x ¹⁴	x ³	x ³	x
		0:00	08:00	Drug administration (labelled compound)							
		0:20	08:20			x					
		0:40	08:40			x					
		1:00	09:00		x ¹⁶	x			x	x	
		2:00	10:00	240 mL water intake		x					
		3:00	11:00			x					
		4:00	12:00	Lunch, 240 mL water intake ⁶	x ¹⁶	x	+		x	x	
		6:00	14:00			x					
		8:00	16:00		x ¹⁶	x	+				
		10:00	18:00	Dinner ⁶		x					
		12:00	20:00	Snack ⁶		x	+		x	x	
		2	24:00	08:00	x ^{16,17}	x	+	+	x	x	
			36:00	20:00		x					
		3	48:00	08:00		x	+	+			
		4	72:00	08:00		x	+	+			
		5	96:00	08:00		x	+	+			
		6	120:00	08:00		x	+	+			
		7	144:00	08:00		x	+	+			
		8	168:00	08:00	B ⁸		+	+	x	x	
		9	192:00	08:00		x	+	+			
		10	216:00	08:00			+	+			
		11	240:00	08:00		x	+	+			
		12	264:00	08:00			+	+			
		13	288:00	08:00		x	+	+			
		14	312:00	08:00			+	+			
		15	336:00	08:00	Discharge from trial site ¹⁵	B ⁸	x	▼	▼	x	x

Proprietary confidential information © 2020 Boehringer Ingelheim International GmbH or one or more of its affiliated companies

Visit	Day	Planned time (relative to drug administration) [h:min]	Approximate clock time of actual day [h:min]	Event and comment	Safety laboratory	PK _{blood/plasma} ^{2,9}	PK _{urine} ⁵	PK _{faeces} ⁴	Vital signs (BP, PR, ECG)	Questioning for AEs & concomitant medication
2	20	461:00	13:00	Start home collection ^{10, 11}				▲		↑
	21	485:00	13:00	Admission to trial site ¹⁰	x ^{16, 17}	x	▲	+		
	22	509:00	13:00	Discharge from trial site ¹⁰			▼		x	
	27	629:00	13:00	Start home collection ^{10, 11}				▲		
	28	653:00	13:00	Admission to trial site ¹⁰	x ^{16, 17}	x	▲	+		
	29	677:00	13:00	Discharge from trial site ¹⁰			▼		x	
	34	797:00	13:00	Start home collection ^{10, 11}				▲		
	35	821:00	13:00	Admission to trial site ¹⁰	x ^{16, 17}	x	▲	+		
	36	845:00	13:00	Discharge from trial site ¹⁰			▼		x	
	41	965:00	13:00	Start home collection ^{10, 11}				▲		
	42	989:00	13:00	Admission to trial site ¹⁰	x ^{16, 17}	x	▲	+		
	43	1013:00	13:00	Discharge from trial site ¹⁰			▼		x	
	48	1133:00	13:00	Start home collection ^{10, 11}				▲		
	49	1157:00	13:00	Admission to trial site ¹⁰	x ^{16, 17}	x	▲	+		
	50	1181:00	13:00	Discharge from trial site ¹⁰			▼		x	
3	16-50			End of trial (EOT) examination ^{7,12,15}	C ¹⁷				x	x

A, B & C: safety laboratory sets (see Table 5.2.3:1)

1. Screening includes subject information, informed consent, physical examination, check of vital signs, ECG, safety laboratory (including drug and virus screening), demographics (including determination of body height and weight, smoking status and alcohol history), relevant medical history, concomitant therapy and review of inclusion/exclusion criteria, neurological examination and suicidality assessment (C-SSRS).
2. Pharmacokinetics (PK): BI 1358894 and metabolites in plasma; [¹⁴C]-radioactivity in whole blood and plasma. At all time points, samples for [¹⁴C]-radioactivity in whole blood and plasma will be taken. Samples for PK assessment of cold BI 1358894 will be collected for all PK samples taken and for its metabolites in plasma which will be collected at the metabolite PK time points in the [Flow Chart](#), after intake of radiolabelled drug on Day 1. PK sampling for the metabolites will continue as long as radioactivity in plasma is above LLOQ (< 30 dpm/mL)
3. The time is approximate; the procedure is to be performed within a time window of 3 h prior to drug administration.
4. All stools (for [¹⁴C]-radioactivity assessment [REDACTED]) will be collected quantitatively from Day 1 in sampling intervals as defined in the [Flow Chart](#) after intake of [¹⁴C] BI 1358894. Thereafter, if warranted, 24 h collections are to be performed on days 21-22, 28-29, 35-36, 42-43, and 49-50. A blank sample will be collected before drug administration on Day 1. Collection of the predose faeces sample will start from approximately -48 h before drug administration. Faeces sampling for [¹⁴C]-radioactivity assessment will be stopped when the release criteria for radioactivity recovery (Section 3.1) have been met (earliest stopping on day 15). “+” means end of last collection interval, start of following collection interval. All samples: planned for determination of [¹⁴C]-radioactivity.
5. Urine collection intervals (for PK/[¹⁴C]-radioactivity assessment [REDACTED] (planned time): on Day -1 or Day 1 predose (blank) sample, on Day 1 prior to start of urine collection voiding of the bladder, and at the intervals defined in the [Flow Chart](#) up to 336 h after drug administration. Thereafter, if warranted, 24 h collections are to be performed on days 21-22, 28-29, 35-36, 42-43, and 49-50. Urine sampling for PK will be stopped when release criteria for radioactivity recovery (Section 3.1) have been met (earliest stopping on day 15). “+” means end of last collection interval, start of following collection interval. All samples: planned for determination of [¹⁴C]-radioactivity, BI 1358894 and its metabolites. [REDACTED]
6. If several actions are indicated at the same time point, the intake of meals will be the last action.

Proprietary confidential information © 2020 Boehringer Ingelheim International GmbH or one or more of its affiliated companies

7. End-of-trial (EOT) examination to be performed within 1 to 7 days after last discharge from the study centre, or, if all once-weekly 24 h sampling periods are needed, prior to discharge on Day 50. EOT examination includes physical examination, vital signs, ECG, safety laboratory, recording of AEs and concomitant therapies, neurological examination and suicidality assessment (C-SSRS).
8. Subjects are to be fasted for at least 10 h before sample is taken.
9. Blood sampling for an individual subject can be stopped if [¹⁴C]-radioactivity in plasma is below limit of detection (<LLOQ 30 dpm/mL) at two consecutive sampling time points for this subject.
10. The planned times for admission, discharge, start and end of the urine and faeces collection intervals are approximate. The procedures are to be performed within a time window of \pm 4 h to the planned time.
11. Subjects are to collect faeces at home within 24 h intervals before admission to once-weekly in-house collection intervals. Home collection intervals: Day 20-21, 27-28, 34-35, 41-42, and 48-49. If faeces are collected in the subsequent in-house collection interval, faeces collected at home will be discarded. If no faeces is collected in the subsequent in-house collection interval (no defecation), faeces collected at home will be used instead for analysis.
12. For definition of the individual subject's end of trial see Section [6.2.3](#)
13. Urine drug and alcohol screening will be done at this time point.
14. Subjects will collect a pre-dose faeces sample at home in specific containers provided by [REDACTED]
15. Confirmation of fitness includes physical and neurological examination, vital signs, ECG, suicidality assessment (C-SSRS) only at Day 15 and EOT, recordings of AEs and concomitant therapies as well as evaluation of safety laboratory assessed on Day 8.
16. At this time point, only a sample for haematocrit measurement is taken.
17. PCR testing for SARS-CoV-2 will be performed at admission on Day – 1, on Day 2, at each admission to the trial site for the 24-h visits and at EOT.

Proprietary confidential information © 2020 Boehringer Ingelheim International GmbH or one or more of its affiliated companies

Flow Chart: Part 2 (Multiple dose)

Visit	Day	Planned time (relative to drug administration) [h:min]	Approximate clock time of actual day [h:min]	Event and comment	Safety laboratory	PK _{plasma} ^{2,9}	PK _{urine} ⁵	12-lead ECG	Vital signs (BP, PR)	Questioning for AEs & concomitant medication
1	-21 to -2			Screening (SCR) ¹	A			x	x	x
2	-1	-21:00	11:00	Admission to trial site	B ^{10, 11}					x
	1	-2:00	06:00			x ³	x ³	x ³	x ³	
		-0:30	07:30	Standard continental breakfast						
		0:00	08:00	Drug administration						
		0:30	08:30			x				
		1:00	09:00			x				
		2:00	10:00			x				
		4:00	12:00	Lunch ⁶		x				
		5:00	13:00			x				
		6:00	14:00			x				
		7:00	15:00			x				
		8:00	16:00			x				
		10:00	18:00	Dinner ⁶		x				
		12:00	20:00	Snack ⁶		x				
		14:00	22:00			x				
	2	24:00	08:00	Drug administration ¹²	x ¹¹	x ³	x ³			
	3	48:00	08:00	Drug administration ¹²						
	4	72:00	08:00	Drug administration ¹²						
	5	96:00	08:00	Drug administration ¹²						
	6	120:00	08:00	Drug administration ¹²						
	7	144:00	08:00	Drug administration ¹²	B ⁸	x ³	x ³	x ³	x ³	
		144:30	08:30			x				
		145:00	09:00			x				
		146:00	10:00			x				
		148:00	12:00	Lunch ⁶		x				
		149:00	13:00			x				
		150:00	14:00			x				
		151:00	15:00			x				
		152:00	16:00			x				
		154:00	18:00	Dinner ⁶		x				
		156:00	20:00	Snack ⁶		x				
		158:00	22:00			x				
	8	168:00	08:00	Drug administration ¹²		x ³				
	9	192:00	08:00	Drug administration ¹²		x ³	x ³			
	10	216:00	08:00	Drug administration ¹²						
	11	240:00	08:00	Drug administration ¹²		x ³	x ³			
	12	264:00	08:00	Drug administration ¹²						
	13	288:00	08:00	Drug administration ¹²						
	14	312:00	08:00	Drug administration ¹²	B ⁸	x ³	x ³	x ³	x ³	
		312:30	08:30			x				
		313:00	09:00			x				
		314:00	10:00			x				
		316:00	12:00	Lunch ⁶		x				
		317:00	13:00			x				

Proprietary confidential information © 2020 Boehringer Ingelheim International GmbH or one or more of its affiliated companies

Visit	Day	Planned time (relative to drug administration) [h:min]	Approximate clock time of actual day [h:min]	Event and comment	Safety laboratory	PK _{plasma} ^{2,9}	PK _{urine} ⁵	12-lead ECG	Vital signs (BP, PR)	Questioning for AEs & concomitant medication
		318:00	14:00			x				
		319:00	15:00			x				
		320:00	16:00			x				
		322:00	18:00	Dinner ⁶		x				
		324:00	20:00	Snack ⁶		x				
		326:00	22:00			x				
	15	336:00	08:00	Drug administration ¹²		x ³	x ³			
	16	360:00	08:00	Drug administration ¹²						
	17	384:00	08:00	Drug administration ¹²		x ³	x ³			
	18	408:00	08:00	Drug administration ¹²						
	19	432:00	08:00	Drug administration ¹²		x ³	x ³			
	20	456:00	08:00	Drug administration ¹²						
	21	480:00	08:00	Drug administration ¹²	B ⁸	x ³	x ³	x ³	x ³	
		480:30	08:30			x				
		481:00	09:00			x				
		482:00	10:00			x				
		484:00	12:00	Lunch ⁶		x				
		485:00	13:00			x				
		486:00	14:00			x				
		487:00	15:00			x				
		488:00	16:00			x				
		490:00	18:00	Dinner ⁶		x				
		492:00	20:00	Snack ⁶		x				
		494:00	22:00			x				
	22	504:00	08:00			x				
	23	528:00	08:00			x				
	25	576:00	08:00			x				
	27	624:00	08:00	Breakfast ⁶ (voluntary), Discharge from trial site after confirmation of fitness ⁴	B ⁸	x		x	x	
	30	696:00	08:00	Ambulatory visit		x				x
	34	792:00	08:00	Ambulatory visit		x				x
	37	864:00	08:00	Ambulatory visit		x				x
	41	960:00	08:00	Ambulatory visit		x				x
	44	1032:00	08:00	Ambulatory visit		x				x
	48	1128:00	08:00	Ambulatory visit		x				x
	51	1200:00	08:00	Ambulatory visit		x				x
	55	1296:00	08:00	Ambulatory visit		x				x
	58	1368:00	08:00	Ambulatory visit		x				x
3	62			End of trial (EOT) examination ^{7,9}	C ¹¹	x		x	x	x

A, B & C: safety laboratory sets (see Table 5.2.3: 1)

1. Screening includes subject information, informed consent, physical examination, check of vital signs, ECG, safety laboratory (including drug and virus screening), demographics (including determination of body height and weight, smoking status and alcohol history), relevant medical history, concomitant therapy, review of inclusion/exclusion criteria, neurological examination and suicidality assessment (C-SSRS).
2. Pharmacokinetics (PK): BI 1358894 and metabolite(s) in plasma.

Proprietary confidential information © 2020 Boehringer Ingelheim International GmbH or one or more of its affiliated companies

3. The time is approximate; the procedure is to be performed within a time window of 3 h prior to drug administration.
4. Confirmation of fitness includes physical and neurological examination, vital signs, ECG, suicidality assessment (C-SSRS), recordings of AEs and concomitant therapies as well as evaluation of safety laboratory assessed on Day 21.
5. Urine collection (for PK assessment [REDACTED] planned time): A predose urine sample collected and stored on Day -1 or Day 1 predose will serve as blank sample. Urine collection is to be performed as described in the [Flow Chart](#).
6. If several actions are indicated at the same time point, the intake of meals will be the last action.
7. End-of-trial (EOT) examination includes physical examination, vital signs, ECG, safety laboratory, recording of AEs and concomitant therapies, neurological examination and suicidality assessment (C-SSRS). The EOT assessments will be performed after the last PK sample on Day 62 has been taken.
8. Subjects are to be fasted for at least 10 h before sample is taken.
9. For definition of the individual subject's end of trial see Section [6.2.3](#)
10. Urine drug and alcohol screening will be done at this time point.
11. PCR testing for SARS-CoV-2 will be performed at admission on Day – 1, on Day 2 and at EOT.
12. A standard continental breakfast will be provided approx. 30 min prior to each daily drug administration from Day 1 to Day 21.

TABLE OF CONTENTS

TITLE PAGE	1
CLINICAL TRIAL PROTOCOL SYNOPSIS	2
FLOW CHART	5
TABLE OF CONTENTS	11
ABBREVIATIONS	15
1. INTRODUCTION.....	18
1.1 MEDICAL BACKGROUND	18
1.2 DRUG PROFILE	19
1.2.1 BI 1358894	19
1.2.2 Residual Effect Period	22
1.3 RATIONALE FOR PERFORMING THE TRIAL	22
1.4 BENEFIT - RISK ASSESSMENT	22
2. TRIAL OBJECTIVES AND ENDPOINTS.....	24
2.1 MAIN OBJECTIVES, PRIMARY AND SECONDARY ENDPOINTS	24
2.1.1 Main objectives.....	24
2.1.2 Primary endpoints	24
2.1.3 Secondary endpoints.....	24
	
2.2.2.4 Safety and tolerability	28
3. DESCRIPTION OF DESIGN AND TRIAL POPULATION.....	29
3.1 OVERALL TRIAL DESIGN AND PLAN	29
3.2 DISCUSSION OF TRIAL DESIGN, INCLUDING THE CHOICE OF CONTROL GROUP	30
3.3 SELECTION OF TRIAL POPULATION	30
3.3.1 Main diagnosis for trial entry	30
3.3.2 Inclusion criteria	30
3.3.3 Exclusion criteria	31
3.3.4 Withdrawal of subjects from treatment or assessments	33

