Irrespective of whether release criteria have been met or not after collection interval Day 49-50, no further collections are planned.

Part 2:

Non-radiolabelled compound will be administered at the site from Day 1 to Day 21. Subjects will remain at the study site from admission on Day – 1 up to discharge on Day 27.

An overview of all relevant trial activities is provided in the [Flow Chart](#). For visit schedule and details of trial procedures at selected visits, refer to Sections [6.1](#) and [6.2](#), respectively.

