3.3.4.1 Discontinuation of trial treatment

An individual subject will discontinue trial treatment if:

1. The subject wants to discontinue trial treatment, without the need to justify the decision
2. The subject has repeatedly shown to be non-compliant with important trial procedures and, in the opinion of both, the investigator and sponsor representative, is not willing or able to adhere to the trial requirements in the future.
3. The subject needs to take concomitant medication that interferes with the investigational medicinal product or other trial treatment
4. The subject can no longer receive trial treatment for medical reasons (such as surgery, adverse events [AEs], or diseases)
5. The subject has an elevation of AST and/or ALT ≥ 3 -fold ULN and an elevation of total bilirubin ≥ 2 -fold ULN (measured in the same blood sample) and/or needs to be followed up according to the DILI checklist provided in the ISF
6. The subject shows a raised CRP level of > 30.0 mg/L
7. An AE or clinically significant laboratory change or abnormality occurred that the investigator judges to warrant discontinuation of treatment. This may include cases of sustained symptomatic hypotension (BP $< 90/50$ mmHg) or hypertension (BP $> 180/100$ mmHg) or of clinically relevant changes in ECG requiring intervention as well as unexplained liver enzyme elevations at any time during the trial.
8. The subject experiences a serious adverse reaction which is considered at least possibly related to the IMP administration

In addition to these criteria, the investigator may discontinue subjects at any time based on his or her clinical judgment.

Proprietary confidential information © 2020 Boehringer Ingelheim International GmbH or one or more of its affiliated companies

Even if the trial treatment is discontinued, the subject remains in the trial and, given his/her agreement, will undergo the procedures for early treatment discontinuation and follow up as outlined in the [Flow Chart](#) and Section [6.2.3](#).

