5.2.5 Other safety parameters

5.2.5.1 Suicidality assessment

The C-SSRS is a semi-structured, investigator-rated interview, developed by clinical experts in cooperation with the FDA, assessing both suicidal behavior and suicidal ideation. It does not give a global score, but provides some categorical and some severity information specifically for behavior and ideation.

The C-SSRS interview may be administered by any type of physician, psychologist, clinical social worker, mental health counselor, nurse, or coordinator with C-SSRS training. It has a typical duration of five minutes, and causes only a low burden on subjects. At a minimum, the interview consists of 2 screening questions related to suicidal ideation and 4 related to suicidal behavior, and may be expanded to up to 17 items in case of positive responses. Free text entries are allowed for; the investigator has to directly evaluate the scale and write a report.

The C-SSRS has been widely used in large multinational clinical trials. The C-SSRS will be administered at the screening visit (using the ‘screening / baseline’ version) with the aim to exclude subjects with active moderate or severe symptomatology within a specified time prior to the screening or baseline visit. The life time history of suicidal ideation and behavior will also be recorded.

After the baseline visit the assessment ‘since last visit’ will be performed at the time points indicated in the [Flow Chart](#). The investigator is to review positive and negative reports for plausibility and clinical relevance. Doubtful reports may be repeated or reports may be validated by a consulting psychiatrist. If there is a confirmed positive report of suicidal behavior or suicidal ideation type 4 or 5 after start of trial, the investigator is to immediately interview the subject during the clinic visit, and/or is to consult a psychiatrist.

If the positive report is confirmed, appropriate actions for the subject’s safety have to be initiated.

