All C-SSRS reports of suicidal ideation type 4 or 5 and all reports of suicidal behaviour must be reported as separate SAEs by the investigator. For “Self-injurious behaviour, no suicidal intent” (Type 11) standard AE/SAE reporting rules are to be applied. For each negative report (suicidal ideation type 1, 2, or 3) after start of the trial, the investigator is to decide based on clinical judgment whether it represents an AE as defined in the protocol, and if it is considered an AE then it must be reported accordingly.

The original English version can be found in Appendix [10.1](#).

Proprietary confidential information © 2020 Boehringer Ingelheim International GmbH or one or more of its affiliated companies

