10.3 COVID-19 SITE SPECIFIC MEASURES

This section contains a risk assessment for study 1402-0015 with BI 1358894 due to the circumstances created by the coronavirus disease-19 (COVID-19) pandemic. In addition, the document summarizes the mitigation approaches to be followed to minimize the risk of spreading severe acute respiratory syndrome coronavirus 2 (SARS CoV-2).

Risk Assessment

BI 1358894 is a TRPC4/5 inhibitor in development for treatment of Major Depressive Disorder and for the treatment of Borderline Personality Disorder (BoPD). It is expected that treatment with BI 1358894 has the potential to improve affective symptoms and emotion control, especially in patients with MDD who inadequately respond to the current standard of care (SSRI; SNRI) and in patients with BoPD, where no approved drug treatment is currently available

Relevant information on the product

BI 1358894 is a highly potent and selective TRPC4/5 Inhibitor (transient receptor potential cation channel, subfamily C, members 4 and 5). It has the potential to address core symptoms of MDD and BoPD as it targets TRPC4/5 ion channels. TRPC4 and TRPC5 are highly expressed in pyramidal neurons of the amygdala in the frontal cortex, hippocampus, and hypothalamus, brain areas that are involved in circuits contributing to emotional control. BI 1358894 is thought to decrease neuronal excitability leading to normalization of the activation state of limbic circuits, which are known to be important for emotional control.

BI 1358894 is characterised by high bioavailability after oral intake, moderate volume of distribution, low clearance and long terminal half-life. Excretion occurs almost exclusively via faeces. After administration of BI 1358894 tablets, maximum plasma concentrations of BI 1358894 occurred around 1 to 5 hours after dosing. The terminal half-life was 41 to 52 hours for blood. Steady state was reached after 11 to 14 days of BI 1358894 dosing.

Currently, repeat dose toxicity studies up to 13 weeks revealed toxicologically relevant effects on the skin (mice), Harderian glands (mice), hepatic function (mice), the vascular system (rats), male genital tract (rats), the Central Nervous System (CNS) function (dogs), and the digestive tract, renal function, and white blood cell parameters (mice, rats and dogs).

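### Part 2 schedules no C-SSRS interview between screening and Day 27, so none falls on any of a subject's 21 dosing days

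*Protocol*

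**What the plan says.** All references are to the protocol unless the SAP is named.

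- **Status.** Section 2.2.2.4 lists the C-SSRS among the safety and tolerability assessments.
- **Timing.** Flow Chart Part 2 has no C-SSRS column. Footnote 1 places it at screening ("concomitant therapy, review of inclusion/exclusion criteria, neurological examination and suicidality assessment (C-SSRS"). Footnote 4 places it at discharge: "Confirmation of fitness includes physical and neurological examination, vital signs, ECG, suicidality assessment (C-SSRS), recordings of AEs and concomitant therapies". Footnote 4 is attached only to the Day 27 row ("Discharge from trial site after confirmation of fitness"). Footnote 7 places it at the end-of-trial examination on Day 62. Section 5.2.5.1 refers to the Flow Chart for the post-baseline interviews and gives no further days.
- **Dosing.** Section 3.1: "Non-radiolabelled compound will be administered at the site from Day 1 to Day 21".
- **Consequences of a positive report.** Section 5.2.5.1: "If there is a confirmed positive report of suicidal behavior or suicidal ideation type 4 or 5 after start of trial, the investigator is to" interview the subject at once and/or consult a psychiatrist. It adds: "All C-SSRS reports of suicidal ideation type 4 or 5 and all reports of suicidal behaviour must be reported as separate SAEs by the investigator".
- **Rules an SAE can reach.** Section 3.3.4.1 item 8 stops a subject's treatment when "The subject experiences a serious adverse reaction which is considered at least possibly related to the IMP administration". Item 7 covers adverse events that the investigator judges to warrant stopping. Section 3.3.4.3 item 2 terminates the trial for one drug-related SAE. None of these rules names the C-SSRS.
- **Analysis.** SAP Section 7.8.5 lists C-SSRS results without further analysis and says that findings are also reported as adverse events. SAP Section 6.1 assigns events to the screening, on-treatment or follow-up phase.

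**The concern.** The protocol chose a structured suicidality interview for a CNS-active drug and attached prompt action and SAE reporting to a positive result. In Part 2 it then schedules that interview only before the dosing course and after it has ended.

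Two things are at stake for each subject.

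1. **Timeliness.** While he is being dosed, no scheduled C-SSRS result of his own can inform Section 3.3.4.1 or 3.3.4.3. The course is 21 days, against the 14 days reported for the multiple-rising-dose trial. Section 1.2.1 reports 2.5-fold accumulation in the 10 and 25 mg groups, with steady state after about two weeks. Exposure should therefore be highest in the later part of dosing, when no interview is planned.
2. **Attribution.** There is no interview at admission, so the Day 27 interview covers pre-dose and on-drug time together. The SAP's main adverse event displays show the on-treatment phase only, so whether onset fell before or after the first dose decides whether an event appears in them. The since-last-visit form in Appendix 10.1.2, as reproduced, has a date field for the most lethal attempt but none for ideation.

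**Working it through.** The plan states no figure for this interval. The check compares the interview days with the dosing days.

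**Inputs**
- Scheduled C-SSRS days in Part 2: screening (Day -21 to -2), Day 27, Day 62 (footnotes 1, 4 and 7).
- Dosing: Days 1 to 21. First dose at planned time 0 h, last dose at 480 h. Day 27 is at 624 h (Flow Chart Part 2).
- Day numbering has no Day 0: Day -1 is followed by Day 1.
- Interview length: typically five minutes (Section 5.2.5.1). Subjects in Part 2: 8.

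**Step 1, overlap.** None of the scheduled C-SSRS days lies between Day 1 and Day 21: 0 of 21 dosing days.

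**Step 2, delay after dosing.** 624 - 480 = 144 h, and 144 / 24 = 6 days after the last dose. From the first dose it is 624 / 24 = 26 days.

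**Step 3, recall window at Day 27.**
- Screened on Day -2: 2 days to Day 1, plus 26 = 28 days.
- Screened on Day -21: 21 days to Day 1, plus 26 = 47 days.
- Pre-dose share: 2/28 = 7% to 21/47 = 45%.

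**Step 4, effect of interviews on Days -1, 7, 14 and 21.**
- Day -1 to Day 7: 1 + 6 = 7 days.
- Day 7 to 14 and Day 14 to 21: 7 days each.
- Day 21 to 27: 6 days.

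The longest interval between admission and discharge is then 7 days. The pre-dose part of the Day 7 window is one day.

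**Step 5, cost.** 4 interviews x 5 min = 20 min per subject. 20 x 8 = 160 min in total. 4 x 8 = 32 additional evaluations and reports.

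**The case against.** The strongest reply is that dosing is not left without surveillance. Subjects are in-house until Day 27. Section 6.2.2 has adverse events assessed continuously. Section 5.2.6.2.1 has medical staff assess subjects regularly, with specific questions where needed. An event found that way can reach Section 3.3.4.1 items 7 and 8 on any dosing day, and the investigator may stop treatment at any time. All of this stands. A reader might infer that suicidality goes unmonitored during dosing, or that the stopping rules cannot operate then. The documents support neither inference. The gap concerns only the scheduled structured interview.

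Other parts of the reply also stand:

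- **Trial-level rule.** Section 3.3.4.3 applies to the whole trial. A Part 1 subject's Day 15 interview, an early discontinuer's end-of-trial examination or another Part 2 subject's Day 27 interview could reach it while others are still dosing. The documents do not say how dosing is staggered, so the point holds within a subject only.
- **Onset.** A reader might infer that pre-dose and on-drug onset cannot be separated at all. Adverse event records carry a time of onset, and events are asked about at admission, so separation is provided for. What is weak is its basis, which is recall over four to seven weeks.
- **Day 27 is not drug-free.** It lies inside the 14-day residual effect period and the SAP on-treatment phase, which runs to 480 + 336 = 816 h. If decline is mono-exponential at the stated effective half-life of 50 to 70 h, 144 h leaves 0.5^(144/50) = 14% to 0.5^(144/70) = 24%.
- **Low prior risk.** Exclusion criteria 24 and 25 remove subjects with past suicidal behaviour or recent active ideation, and Appendix 10.3 reports no SAE in seven completed trials. The expected yield of extra interviews is probably small, and the documents give no figure for it.
- **Neurological examination.** It follows the same three time points. A reader might infer that it too should be moved onto dosing days. Appendix 10.3 deliberately limits physical examinations to screening, discharge and follow-up, and Section 5.2.5.2 describes the neurological check as a physical one. The schedule agrees with that limit, so only a question to the sponsor is warranted.

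None of this closes the gap. General adverse event questioning is not the structured interview that the protocol selected, and the available text gives no reason for leaving that interview out of the dosing period.

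**Conclusion.** The point holds within each subject. In Part 2 no scheduled C-SSRS falls on any of the 21 dosing days. For a subject who completes dosing, the first since-last-visit interview comes 6 days after the last dose and covers 28 to 47 days by recall, with no interview at admission to mark off the pre-dose period. His own scheduled result therefore cannot inform Sections 3.3.4.1 or 3.3.4.3 while he is being dosed. A subject who stops early is interviewed at his end-of-trial examination, also after dosing has ended.

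This is an inexpensive improvement to safety data and to onset attribution. It is not a contradiction in the protocol and does not affect the pharmacokinetic endpoints. It rests on the planned days in the Flow Chart and on the absence of any C-SSRS time point elsewhere in the available text.

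**What to change.** 1. Add the existing C-SSRS, in its since-last-visit version, to Flow Chart Part 2 at admission (Day -1) and on Days 7, 14 and 21. Subjects are already in-house, and Days 7, 14 and 21 already carry safety laboratory set B, ECG and vital signs. Keep Day 27 and Day 62.
2. Leave the actions after a positive report as written. The change adds no condition on dosing. Ask the sponsor to state how Sections 5.2.5.1, 3.3.4.1 and 3.3.4.3 connect, since the link now runs only through adverse event and SAE reporting.
3. For the neurological examination, ask the sponsor to reconcile its timing with the Appendix 10.3 limit on physical examinations and to give the rationale. No new time point is proposed.

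The cost is a Flow Chart amendment and the interview time computed above. The investigator's evaluation and written report for each interview come on top, and the protocol gives no time for them. No new staff or type of procedure is needed, and Section 5.2.5.1 itself rates the burden on subjects as low.
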